1.0 Objectives

1.1 Study Objectives

The main objective is to compare the test characteristics of the human papillomavirus (HPV) self-sampling kit versus clinician-sampled HPV testing for cervical cancer screening. This study seeks to find out if the HPV self-sampling kit is non-inferior to standard clinician-sampling practices.

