1.2 Primary Study Endpoints

The primary outcomes of this study are to analyze the screening results on self-sampling kits compared to clinician-collected HPV test, Pap smear results, and colposcopy.

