2.2 Previous Data

There have been previous studies about the effectiveness of self-collected samples as an alternative to clinician collected samples. Some studies state that HPV testing is more sensitive than Pap testing.⁵ There is a possibility that these two samples have similar sensitivity.⁶ Based on this information, examining test characteristics and acceptability of each technique is necessary to support larger efforts to make self-sampling available.

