Participants must complete the self-sampling kit within 14 days before or after their colposcopy visit, meaning that there is a 28 day window for participants to collect the sample. A 2nd HPV self-sampling kit will only be mailed if the participant states that she lost or did not receive the first one. Participants will receive a maximum of 2 HPV self-sampling kits.

Once the HPV self-sampling kit has been returned and the survey completed, the study participants will be mailed an incentive in the form of a Greenphire ClinCard, and a thank you letter from the PI. Analysis of the self-sampling specimens will be conducted to determine HPV DNA positivity to compare to the results of the previous Pap test, HPV test, and colposcopy. EMR data will be used to check insurance status, and the date and result of Pap test, HPV test, and colposcopy.

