8.3 Statistical methods

We will conduct Fisher's exact tests to examine our primary study outcome, i.e., concordance/non-inferiority of HPV self-sampling test results versus clinician-sampled test results. Additional analyses of the concordance across test will use Cohen's kappa coefficient. In addition, we will summarize survey results using descriptive analysis, including calculating means, Pearson's correlation coefficients, and Fisher's exact tests.

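### Section 8.3 plans agreement statistics only, with no analysis against the colposcopy outcome, so neither HPV test's accuracy for disease would be estimated

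*Combined protocol and SAP*

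**What the plan says.** Section 1.1 states the aim: "The main objective is to compare the test characteristics of the human papillomavirus (HPV) self-sampling kit versus clinician-sampled HPV testing for cervical cancer screening". It adds a hypothesis: "This study seeks to find out if the HPV self-sampling kit is non-inferior to standard clinician-sampling practices". No margin or metric is attached. Section 2.2 shows that accuracy is within the protocol's own meaning of test characteristics, because it raises sensitivity just before using the term: "There is a possibility that these two samples have similar sensitivity".

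Section 1.2 sets the primary outcomes as self-sample results "compared to clinician-collected HPV test, Pap smear results, and colposcopy". Section 7.1 provides for the data: "EMR data will be used to check insurance status, and the date and result of Pap test, HPV test, and colposcopy".

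Section 8.3 lists the analyses. The primary one is Fisher's exact testing of self-sample against clinician-sample results. Then comes "Additional analyses of the concordance across test will use Cohen's kappa coefficient". The rest concerns the survey. Neither section 8.3 nor any other section plans sensitivity, specificity, predictive values or a paired difference in accuracy, and none says what colposcopy finding counts as disease.

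**The concern.** The objective and the primary outcome look towards disease at colposcopy, while the analysis section looks only at whether results agree. When the self-sample and the clinician sample disagree, what matters for screening is whether the woman has disease. A self-sample that loses only infections without disease and one that loses true cases can give the same agreement, the same kappa and the same Fisher p-value. Someone who followed section 8.3 exactly would finish with a primary comparator named in section 1.2 left unanalysed, and with no evidence on accuracy behind any statement about test characteristics.

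**Working it through.** **1. The plan's own figure.** Section 8.2 gives 30 participants, citing a 5% significance level and 0.80 (written as beta, read here as power). It gives no margin, null or alternative kappa, positivity rate, discordance rate or sidedness, so 30 cannot be reproduced. It is not tied to any accuracy measure. I take 30 completers as given. Every other rate below is an assumption.

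**2. Same agreement, different accuracy.** Assume 21 women positive on both tests, 3 positive on the clinician test only, 0 on the self-sample only, and 6 negative on both.

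- Observed agreement = (21 + 6)/30 = 0.90.
- Chance agreement = (24×21 + 6×9)/900 = 558/900 = 0.62.
- Kappa = (0.90 − 0.62)/(1 − 0.62) = 0.28/0.38 = 0.737.
- Fisher's p is about 0.0001.

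Now let 9 women have disease, all clinician-positive.

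| | 3 discordant women without disease | 3 discordant women with disease |
|---|---|---|
| Kappa | 0.737 | 0.737 |
| Self-sample sensitivity | 9/9 (exact 95% CI 66% to 100%) | 6/9 = 67% (30% to 93%) |
| Clinician sensitivity | 9/9 | 9/9 |

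The planned statistics are identical in the two columns.

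**3. The result does not depend on that table.** Take 20 both positive, 3 self only, 3 clinician only, 4 both negative. Observed agreement = 24/30 = 0.80; chance agreement = (23×23 + 7×7)/900 = 0.642; kappa = 0.158/0.358 = 0.44; Fisher's p = 0.033. With 9 diseased women this one table is compatible with self versus clinician sensitivities of 9/9 v 9/9, 6/9 v 9/9, or 9/9 v 6/9.

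**4. If kappa were computed against disease.** Assume prevalence 30%, sensitivity 95%, specificity 20%. Observed agreement = 0.30×0.95 + 0.70×0.20 = 0.425. The test-positive share = 0.285 + 0.560 = 0.845. Chance agreement = 0.845×0.30 + 0.155×0.70 = 0.362. Kappa = 0.063/0.638 = 0.10. A highly sensitive test gets a kappa near zero, because kappa mixes sensitivity, specificity and prevalence.

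**5. What 30 women can deliver.** An assumed disease share of 20% to 40% gives 6 to 12 cases. When all x of x cases are positive, the exact lower 95% limit is 0.025^(1/x): 0.54 for 6, 0.66 for 9, 0.74 for 12.

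**6. What a formal test would need.** For paired non-inferiority of sensitivity at one-sided 0.05, 80% power and margin 0.10, cases needed = (1.645 + 0.842)² × discordance / 0.10². Discordance of 5% gives 31 and 10% gives 62. Dividing by a disease share of 50% down to 20% gives 62 (31/0.5) to 310 (62/0.2) women enrolled.

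**The case against.** Five points can fairly be made on the other side.

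- Section 8.3 itself equates the primary outcome with concordance and non-inferiority of self versus clinician results, and section 2.2 presents the work as support for larger efforts. On that reading the main comparison is analysed. This stands in part: the comparison between the two HPV tests is planned, and it is the comparison with colposcopy that has no method.
- A reader might infer that section 8.3 plans kappa between HPV results and colposcopy. The text does not name colposcopy or Pap as kappa comparators, and section 8.2 speaks of two methods. The calculation in step 4 is therefore a caution in case kappa is used that way, and does not criticise a stated analysis.
- A reader might infer that every completer will have a colposcopy result, with histology already on file. The documents do not establish either. Completion and payment (sections 7.1, 7.2.3 and 13.0) turn on the returned kit and the survey, and biopsy and histology are not mentioned. Nor is a clinician HPV result guaranteed, because entry is on an abnormal Pap/HPV test (section 3.1).
- Selection distorts accuracy. Among women referred on a positive HPV test, clinician sensitivity is 100% and specificity 0% by construction. The self-minus-clinician difference can then only be zero or negative in cases, and zero or positive in non-cases. This stands, and it limits how the estimates may be used.
- Thirty women give imprecise estimates. That is true. It argues for descriptive reporting with intervals, and does not justify leaving the colposcopy comparison unanalysed.

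**Conclusion.** The concern holds as a gap in the analysis plan. Sections 1.1 and 1.2 call for test characteristics and a comparison with colposcopy, and section 8.3 supplies no analysis against the colposcopy outcome. Agreement statistics cannot fill the gap: the same kappa of 0.74 fits self-sample sensitivity of 9/9 or 6/9. That contrast rests on assumed tables and an assumed 9 cases, chosen to show two extremes, and does not predict the trial's data. The logical point does not depend on those values.

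It would be too strong to infer that the whole main objective goes unanswered, since self versus clinician results are compared. It would be equally wrong to infer that adding accuracy estimates would rescue a non-inferiority claim on accuracy. Selection at entry inflates the clinician test's sensitivity, depresses its specificity and biases both paired differences, and 30 women are too few under the assumptions in step 6. This is a change that should be made before results are seen.

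**What to change.** Add to section 8.3, for women with a colposcopy result:

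1. A disease definition fixed in advance and based on the result in the medical record. CIN2 or worse, where histology is recorded, is a natural choice because it is the threshold in the title of the paired screen-positive trial in the reference list. State a rule for women without biopsy, with a sensitivity analysis.
2. Sensitivity and specificity of the self-sample with exact 95% intervals, and the same for the clinician HPV test where a result exists.
3. A table of each discordant self/clinician pair by colposcopy outcome.
4. A statement that these results are descriptive and apply to a referred population; that entry on an abnormal Pap/HPV result inflates clinician sensitivity, depresses clinician specificity and biases both paired differences; and that no non-inferiority conclusion on accuracy will be drawn.
5. If kappa is applied to Pap or colposcopy, a note that it is not a test characteristic.

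If concordance alone is intended, sections 1.1 and 1.2 should be narrowed to say so.

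The cost is wording and a few tables, with no extra participants. Histology may have to be added as an extracted field. The intervals will be wide, as step 5 shows.

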9.0 Data and Safety Monitoring Plan

9.1 Periodic evaluation of data

Not applicable.

9.2 Data that are reviewed

Not applicable.

9.3 Method of collection of safety information

Not applicable.

9.4 Frequency of data collection

Not applicable.

9.5 Individuals reviewing the data

Not applicable.

9.6 Frequency of review of cumulative data

Not applicable.

9.7 Statistical tests

Not applicable.

9.8 Suspension of research

Not applicable.

10.0 Risks

Potential risks associated with this research are minimal. Loss of confidentiality is a risk of participation. All information entered into REDCap will be password protected with limited access to specific members of the study team. There may also be risks from participants misusing the self-sampling kit. This may cause minor discomfort if used improperly.

11.0 Potential Benefits to Subjects and Others

11.1 Potential Benefits to Subjects

None

11.2 Potential Benefits to Others

Understanding how the results of the HPV self-sampling kit compare to clinician-collected HPV tests, Pap smears, and colposcopies will ultimately help to create a better screening process. If the findings are similar across tests, HPV self-sampling may emerge as an effective option for cervical cancer screening among underserved populations without routine access to preventive healthcare.

12.0 Sharing Results with Subjects

Not applicable.

13.0 Subject Payment and/or Travel Reimbursements

\$15 via Greenphire ClinCard. After the participant completes the follow-up survey they will be asked to provide the information necessary in order to set up the Greenphire ClinCard. Once the study team receives confirmation that their completed kit was received by PSH, the study team will mail the clinCard to the participant at their preferred address along with the thank you letter.

14.0 Economic Burden to Subjects

14.1 Costs

Not applicable

14.2 Compensation for research-related injury

Not applicable

15.0 Resources Available

15.1 Facilities and locations

Participants will be identified from participating Family and Community Medicine and OBGYN clinics at PSH when they are determined to have abnormal findings on Pap/HPV test that requires a colposcopy for follow-up. Physicians will perform the colposcopy per standard clinical guidelines. Self-sampling kits will be mailed into a PSH lab for analysis with supplies given by the study team. Afterwards, a study team member will collect survey data from participants over the phone.

15.2 Feasibility of recruiting the required number of subjects

Among the PSH study clinics, at least 18 potentially-eligible patients receive a colposcopy each month. All potentially-eligible patients will be invited to join the study, and they will be screened and consented if there are eligible. 30 subjects will be enrolled into the study. Among the 120 invited to participate in this study, we expect 50% (60) to agree to participate and meet eligibility. This should provide a large enough sample size to obtain 30 participants who complete all study procedures. Based on these figures, it will take approximately 7 months to invite 120 subjects and enroll 30 participants who complete all study procedures.

15.3 PI Time devoted to conducting the research

The PI will use dedicated research time to conduct this research.

15.4 Availability of medical or psychological resources

Not applicable.

15.5 Process for informing Study Team

The research team will meet regularly to discuss this study, its procedures, and any issues that may arise.

16.0 Other Approvals

16.1 Other Approvals from External Entities

Not applicable.

16.2 Internal PSU Committee Approvals

Check all that apply:

- Anatomic Pathology – Penn State Health only** – Research involves the collection of tissues or use of pathologic specimens. Upload a copy of “HRP-902 - Human Tissue For Research Form” in CATS IRB.
- Animal Care and Use – All campuses** – Human research involves animals and humans or the use of human tissues in animals

- Biosafety – All campuses** – Research involves biohazardous materials (human biological specimens in a PSU research lab, biological toxins, carcinogens, infectious agents, recombinant viruses or DNA or gene therapy).
- Clinical Laboratories – Penn State Health only** – Collection, processing and/or storage of extra tubes of body fluid specimens for research purposes by the Clinical Laboratories; and/or use of body fluids that had been collected for clinical purposes but are no longer needed for clinical use. Upload a copy of “HRP-901 - Human Body Fluids for Research Form” in CATS IRB.
- Clinical Research Center (CRC) Advisory Committee – All campuses** – Research involves the use of CRC services in any way.
- Conflict of Interest Review – All campuses** – Research has one or more of study team members indicated as having a financial interest.
- Radiation Safety – Penn State Health only** – Research involves research-related radiation procedures. All research involving radiation procedures (standard of care and/or research-related) must upload a copy of “HRP-903 - Radiation Review Form” in CATS IRB.
- IND/IDE Audit – All campuses** – Research in which the PSU researcher holds the IND or IDE or intends to hold the IND or IDE.
- Scientific Review – Penn State Health only** – All investigator-written research studies requiring review by the convened IRB must provide documentation of scientific review with the IRB submission. The scientific review requirement may be fulfilled by one of the following: (1) external peer-review process; (2) department/institute scientific review committee; or (3) scientific review by the Clinical Research Center Advisory committee. NOTE: Review by the Penn State Health Cancer Institute (PSCI) Protocol Review Committee or the PSCI Disease Team is required if the study involves cancer prevention studies or cancer patients, records and/or tissues. For more information about this requirement see the IRB website.

17.0 Multi-Site Study

17.1 Other sites

Not applicable.

17.2 Communication Plans

Not applicable.

17.3 Data Submission and Security Plan

Not applicable.

17.4 Subject Enrollment

Not applicable.

17.5 Reporting of Adverse Events and New Information

Not applicable.

17.6 Audit and Monitoring Plans

Not applicable.

18.0 Adverse Event Reporting

18.1 Reporting Adverse Reactions and Unanticipated Problems to the Responsible IRB

In accordance with applicable policies of The Pennsylvania State University Institutional Review Board (IRB), the investigator will report, to the IRB, any observed or reported harm (adverse event) experienced by a subject or other individual, which in the opinion of the investigator is determined to be (1) unexpected; and (2) probably related to the research procedures. Harms (adverse events) will be submitted to the IRB in accordance with the IRB policies and procedures.

19.0 Study Monitoring, Auditing and Inspecting

19.1 Auditing and Inspecting

The investigator will permit study-related monitoring, audits, and inspections by the Penn State quality assurance program office(s), IRB, the sponsor, and government regulatory bodies, of all study related documents (e.g., source documents, regulatory documents, data collection instruments, study data etc.). The investigator will ensure the capability for inspections of applicable study-related facilities (e.g., pharmacy, diagnostic laboratory, etc.).

20.0 Future Undetermined Research: Data and Specimen Banking

20.1 Data and/or specimens being stored

Not Applicable

20.2 Location of storage

Not Applicable

20.3 Duration of storage

Not Applicable

20.4 Access to data and/or specimens

Not Applicable

20.5 Procedures to release data or specimens

Not Applicable

20.6 Process for returning results

Not Applicable

